10.5.2 Secondary Analyses

Complete response rate, overall response rate (CR + CRh), MRD negativity rate in patients achieving a CR or CRh, allogeneic HCT rate, and rates of adverse events will be reported using descriptive statistics. Relapse-free survival and overall survival will be estimated using the Kaplan-Meier method. Correlation between PD-L1 and PD-L2 expression and response to the combination of blinatumomab and pembrolizumab and correlation of changes in PD-L1 and PD-L2 expression with cytokine response will be evaluated with Chi-squared analysis.

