
Pembrolizumab is a potent and highly selective humanized monoclonal antibody (mAb) of the

IgG4/kappa isotype designed to directly block the interaction between PD-1 and its ligands, PD-L1 and PD-L2. Keytruda™ (pembrolizumab) has recently been approved in the United States for the treatment of patients with non-small cell lung cancer or those with unresectable or metastatic melanoma and disease progression following ipilimumab and, if BRAF V600 mutation positive, a BRAF inhibitor.

PD-1 inhibitors including pembrolizumab have promising activity in solid tumors although their activity in acute leukemia is unknown. A Phase Ib/II study of pembrolizumab in relapsed/refractory hematologic malignancies is ongoing. PD-L1, but not PD-L2, is expressed in a subset of ALL primary cells and in most lymphoid leukemia/lymphoma cell lines [11,12]. PD-L1 also tends to be upregulated in the setting of relapsed malignancies including ALL [13,14]. IFN-gamma and TNF-alpha cause upregulation of PD-L1 in acute leukemia [15] which may potentially contribute to resistance to the effects of blinatumomab given the high expression of IFN-gamma, TNF-alpha and other inflammatory cytokines with blinatumomab treatment. Taken together, pembrolizumab holds promise to augment the effect of blinatumomab in patients with relapsed or refractory B-lineage ALL.

Pembrolizumab is generally well tolerated as monotherapy with principal adverse events being rare immune checkpoint blockade-related toxicities. Adverse events in 411 melanoma patients included pneumonitis in 2.9% (0.2% Grade 3), immune-mediated colitis in 1% (0.5% Grade 3), hepatitis in 0.5% (0.2% Grade 4), hypophysitis in 0.5% (0.2% Grade 4), hyperthyroidism in 1.2% (0.2% Grade 3), hypothyroidism in 8.3% (0.2 % Grade 3), type I diabetes mellitus, and immune-mediated nephritis in 0.7% (0.5% Grade 3 or 4). Treatment with prednisone 40 mg or greater per day led to resolution of symptoms in the large majority of patients. Infusion reactions are rare with pembrolizumab but may occur. The effect of pembrolizumab on the developing fetus is unknown.

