1.4.2 Cytokine studies

Cytokine release syndrome is the principal life-threatening event associated with blinatumomab exposure. In the MRD+ population, Klinger et al. showed the cytokine elevations including IL-2, IL-6, IL-10, TNF- α , and interferon- γ peak about 8-16 hours after starting blinatumomab and subsequently decrease reaching near baseline levels by 48 hours after the start of infusion [9]. More prolonged and severe cytokine elevation lasting days can occur in patients with a high disease burden leading to potentially fatal cytokine release syndrome [10]. Numerous cytokines including IL-2, IL-7, IL-15, IL-21, TNF- α , and interferon- γ are known to lead to upregulation of

PD-L1 and PD-L2 to help negative modulate immune responses. This process may have untoward effects in terms of treatment with immunotherapies such as blinatumomab where maximal T-cell activation in response to drug may be needed to eradicate disease. For this study, we plan to study the pattern of inflammatory cytokine release after blinatumomab alone and the combination of blinatumomab and pembrolizumab and to correlate cytokine release with changes in lymphoblast and bone marrow PD-L1 and PD-L2 expression.

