2.3 Exploratory Objectives

- 2.3.1** To determine PD-1 expression on T-cells and PD-L1 and PD-L2 protein expression on lymphoblasts at diagnosis and in response to therapy
- 2.3.2** To determine changes in bone marrow and peripheral blood T-cell populations in response to therapy with blinatumomab and the combination of blinatumomab and pembrolizumab.
- 2.3.3** To determine changes in PD-1, PD-L1 and PD-L2 expression with blinatumomab exposure and correlation with disease response.
- 2.3.4** To determine changes in cytokine response with therapy and correlate with PD-1, PD-L1 and PD-L2 expression changes

3. Study Endpoints

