3.3 Exploratory Endpoints

3.3.1 Changes in PD-1 protein expression on T-cells and PD-L1 and PD-L2 protein expression on marrow lymphoblasts will be assessed by flow cytometry and Western blotting.

3.3.2 Changes in bone marrow and peripheral blood T-cell populations by flow cytometry in response to therapy with blinatumomab and the combination of blinatumomab and pembrolizumab.

3.3.3 Levels of T-cell PD-1, and lymphoblast PD-L1 and PD-L2 expression by flow cytometry and Western blotting with study therapy will be correlated with disease response.

3.3.4 Changes in serum cytokines with therapy and correlation with PD-1, PD-L1 and PD-L2 protein expression changes

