6.5.1.2 Lymphoblast PD-L1 and PD-L2 expression by Western Blot (UCSD)

Bone marrow aspirate samples for FACS of lymphoblasts and PD-L1 and PD-L2 expression by Western blotting will be collected at the following time points and shipped to the laboratory of [name], PhD:

At screening
Cycle 1 Day 14

Cycle 1 Day 29 +8 days

In the case of a dry tap, a core biopsy is to be collected.

Complete Sample Collection CRF (Appendix F) for each shipment. Email the completed Sample collection CRF prior to shipment to [contact]

- Make a copy of the form to include with the sample(s)
- Retain the original at the site for your records

Email a de-identified (redacted) pathology report(s) if available. Write the study ID on the top of each page of the pathology report.

Samples to be shipped overnight to the [name] Laboratory for processing and analysis:

[name], PhD
Department of Pathology
University of California San Diego
[name]
[name]
[name]
Ph: [contact]

Email: [contact]

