6.5.1.3 T-cell subsets, PD-1 and PD-L1 expression studies by Flow Cytometry

Bone marrow aspirate and peripheral blood samples for flow cytometry for T-cell subsets, PD-1 on T-cells and PD-L1 on lymphoblasts along with appropriate patient-specific lymphoblast markers.

Minimum flow cytometry panels as follows:

Peripheral blood T-cells:

Panel 1 (identification.activation panel) - live/dead stain, CD3, CD4, CD8, CD16, CD56, OX40, CD137, PD-1, LAG-3, TIM-3

Panel 2 (Treg panel) - live/dead stain, CD4, CD25, FoxP3 (intracellular)

Panel 3 (NK cells) - live/dead stain, CD3, CD4, CD8, CD16, CD56, IFN-g (intracellular), granzyme-B (intracellular)

Bone marrow lymphoblasts: PD-L1, CD19, CD10*, TdT*, 7-AAD

(Note: *lymphoblast markers to be selected based on initial immunophenotype and may also include CD34, cCD22, sCD22, CD24, Pax5, CD79a)

Aspirate samples will be sent for testing at the following time points:

At screening

Cycle 1 Day 14

Cycle 1 Day 29 + 8 days

Cycle 2 Day 29 + 8 days

3-5 mL of bone marrow aspirate and 5 mL peripheral blood to be collected in EDTA (lavender-top) tube and be sent same day by hand delivery or overnight shipping to the laboratory of [name], PhD:

[name], PhD
Department of Pathology
University of California San Diego
[name]
[name]
[name]
Ph: [contact]
Email: [contact]

In the case of a dry tap, a core biopsy is to be collected.

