6.5.1.4 Serum cytokine assays

Peripheral blood Serum Cytokine assays samples will be collected at the following time points in Cycle 1:

Day 1 (prior to blinatumomab)
Day 2 (24 +/- 2 hours after blinatumomab start)
Day 3 (48 hours +/- 2 hours after blinatumomab start)
Day 8 (prior to blinatumomab 28 mcg/day dose)
Day 9 (24 +/- 2 hours after blinatumomab dose increase on Day 8)
Day 10 (48 hours +/- 2 hours after blinatumomab dose increase on Day 8)
Day 15 (prior to pembrolizumab)
Day 16 (24 +/- 2 hours after pembrolizumab Day 15 dose)
Day 17 (48 +/- 2 hours after pembrolizumab Day 15 dose)
Day 21

This study will utilize the Cytokine Human 10-plex panel for Luminex® Platform which measures levels of GM-CSF, TNF- α , IL-2, IL-1 β , IL-4, IL-6, IL-8, IFN- γ , IL-10, IL-5.

Peripheral blood to be collected in 1-10mL EDTA tube. Sample to be processed at 1200g for 10min and the plasma stored at -70C. Samples may be batch shipped after collection of all samples for each patient have been collected. Please ensure that a completed CRF form (appendix F) is included with each sample.

Samples to be shipped to UCSD overnight on dry ice.

Study Coordinator, BMT Clinical Trials
UCSD Moores Cancer Center
[name]
[name]
[contact]

Samples to be stored at the UCSD Moores Cancer Center Clinical Trials office until analyzed in [name] at UCSD.

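### Section 10.5.2 names chi-squared, without cut-points, for exploratory markers and cytokines described as levels, and names no test for PD-1

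*Combined protocol and SAP*

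**What the plan says.** The last sentence of Section 10.5.2 covers two associations: PD-L1/PD-L2 expression with response to the combination, and "correlation of changes in PD-L1 and PD-L2 expression with cytokine response will be evaluated with Chi-squared analysis". The Statistical Methodology line of the Study Summary names no other test of association.

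The data are described as levels:
- Cytokines (6.5.1.4): a 10-plex "Platform which measures levels of GM-CSF" and nine other cytokines, drawn at ten Cycle 1 time points.
- Markers (endpoint 3.3.3): "Levels of T-cell PD-1, and lymphoblast PD-L1 and PD-L2 expression by flow cytometry and Western blotting" are to be correlated with disease response.

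PD-1 is in scope. Objective 2.3.4 reads "To determine changes in cytokine response with therapy and correlate with PD-1, PD-L1 and PD-L2 expression changes", and objective 2.3.3 and endpoints 3.3.3 and 3.3.4 also include it. Section 10.5.2 mentions only PD-L1 and PD-L2.

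The documents are not consistent on the PD-L2 assay. Endpoints 3.3.1 and 3.3.3 name flow cytometry and Western blotting. The sampling sections provide for PD-L2 only by blot: 6.5.1.2 has "Bone marrow aspirate samples for FACS of lymphoblasts and PD-L1 and PD-L2 expression by Western blotting", while the lymphoblast flow panel in 6.5.1.3 is "Bone marrow lymphoblasts: PD-L1, CD19, CD10*, TdT*, 7-AAD". That panel is introduced as a minimum, so it does not exclude PD-L2.

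Section 10.5.1 limits the sample to 24 efficacy-evaluable patients, or 18 if the trial stops after its first efficacy stage.

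**The concern.** A chi-squared test needs categories. Applied to levels, it needs a cut on the marker and, for the cytokine analysis, a second cut on the cytokine. The plan gives neither. It also does not define cytokine response, say which time points are compared, or say whether a continuity correction is used.

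Two things follow. Dichotomising discards information that is scarce with 18 to 24 patients. And while the cuts are open they can be settled after the data are seen, in which case a nominal 0.05 no longer describes the error rate.

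These analyses bear on the trial's rationale. Section 1.2.2 states that "IFN-gamma and TNF-alpha cause upregulation of PD-L1 in acute leukemia" and suggests that this contributes to blinatumomab resistance. Section 1.4.2 adds that "we plan to study the pattern of inflammatory cytokine release after blinatumomab alone and the combination of blinatumomab and pembrolizumab". A weak or flexible analysis would leave that mechanism poorly examined.

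**Working it through.** **Plan's own figures.** The plan gives no figure for these correlations. The two-stage design in 10.5.1 is used here only as the source of n = 18 or 24. Its rule (stop at 7 or fewer of 18; reject at 11 or more of 24) reproduces: type I error 0.0499, power 0.8014, early termination 0.8800, against the stated 0.05, 0.80 and 0.88.

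**Assumptions, none from the documents.** Normal data, complete at n = 24 or 18; two-sided 0.05; true correlation 0.3 to 0.6 for marker against cytokine; a 1 SD difference for marker against response.

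**1. Median split on both variables: what the test does.** Let a be the number of patients high on both and k = n/2. All margins equal k, so X² = n(a² − (k − a)²)²/k⁴, compared with 3.84.
- n = 24: a = 8 gives 24 × (64 − 16)²/12⁴ = 2.67; a = 9 gives 24 × (81 − 9)²/12⁴ = 6.00. Reject at a ≥ 9 or a ≤ 3. Exact size = 2 × (48,400 + 4,356 + 144 + 1)/2,704,156 = 0.039.
- n = 18: a = 6 gives 18 × (36 − 9)²/9⁴ = 2.00; a = 7 gives 18 × (49 − 4)²/9⁴ = 5.56. Reject at a ≥ 7 or a ≤ 2. Exact size = 2 × (1,296 + 81 + 1)/48,620 = 0.057.

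The continuity correction leaves the n = 24 rule unchanged (a = 9 gives 24 × (72 − 12)²/12⁴ = 4.17). At n = 18 it removes a = 7 (18 × (45 − 9)²/9⁴ = 3.56).

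**2. Power, marker change against cytokine change.** 40,000 simulated data sets per setting, Spearman / uncorrected chi-squared:

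| Correlation | n = 24 | Share kept | n = 18 | Share kept |
|---|---|---|---|---|
| 0.3 | 0.268 / 0.128 | 48% | 0.205 / 0.138 | 67% |
| 0.4 | 0.450 / 0.207 | 46% | 0.342 / 0.206 | 60% |
| 0.5 | 0.660 / 0.326 | 49% | 0.522 / 0.302 | 58% |
| 0.6 | 0.849 / 0.474 | 56% | 0.717 / 0.428 | 60% |

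Repeat simulations at 0.5 gave 0.65 to 0.67 against 0.32 to 0.33 (n = 24), hence the rounded 0.65 and 0.32. Sizes differ slightly from 0.05: the n = 24 gap is a little overstated (size 0.039) and the n = 18 gap a little understated (0.057). With the continuity correction, power at n = 18 and correlation 0.5 falls to about 0.06.

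**3. Cuts chosen after seeing the data, marker against cytokine, no true association.** Take the largest X² over every pair of cuts leaving at least 25% of patients on each side. That is cuts after ranks 6 to 18 at n = 24 (13 × 13 = 169 tables) and 5 to 13 at n = 18 (9 × 9 = 81).
- Uncorrected: 0.75 (n = 24), 0.61 (n = 18).
- Continuity-corrected: 0.37, 0.25.
- Choosing only among tertile and median cuts, uncorrected: 0.25, 0.44.

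**4. Marker against response.** With a fixed median cut the uncorrected test has exact size 0.027 to 0.131 across 8 to 13 responders of 24, or 5 to 7 of 18. Averaged over the two-stage design, size is 0.059, 0.069 and 0.065 at true response rates 0.29, 0.40 and 0.54 (0.011 to 0.020 with continuity correction). Average power, exact Wilcoxon / chi-squared, is 0.378/0.315, 0.485/0.431 and 0.564/0.479, so 83 to 89% is kept. With a data-chosen cut (at least 25% each side) the averaged error is 0.21 to 0.26.

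**The case against.** The strongest defence is that nothing is decided by these analyses. The objectives are labelled exploratory, 10.5.2 attaches no alpha, hypothesis or power to the correlations, and the levels will still exist and can be analysed as levels later. All of that stands, and it is why the point is minor. But a switch of method after the data are in would itself be unplanned, which a sentence written now avoids.

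A reader might infer that cut-points will be tuned to the data. No section says so. The rates in step 3 describe an analyst who searches every allowed cut and reports the best, and they depend heavily on the continuity correction, about which the plan is silent. They bound the risk; they do not predict it.

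A reader might also infer that chi-squared always loses power. For marker against response this depends on the version. At 13 responders of 24 and a 1 SD shift, uncorrected chi-squared has power 0.61 against 0.60 for the exact rank-sum test, but only because its true size there is 0.10. The continuity-corrected version has power 0.28.

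Finally, the sampling sections tempt one to say that PD-L2 is measured by blot alone and is therefore a yes/no marker. Endpoints 3.3.1 and 3.3.3 contradict the first part, and 3.3.3 speaks of levels. The plan does not say how blots are quantified, so a binary reading is possible but not established.

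**Conclusion.** The point holds as a minor improvement to the exploratory analyses. The named test does not fit data described as levels unless cut-points are added, none are given, and PD-1 lacks a named test. That does not mean PD-1 will go unanalysed. Neither the primary response analysis nor the sample size is touched.

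The cost of a fixed median split is clearest for marker against cytokine: about half of Spearman's power at 24 patients and about 60% at 18, over correlations of 0.3 to 0.6. For marker against response it is smaller and comes with an error rate that moves with the number of responders. The possible inflation from open cuts is larger but conditional on conduct the plan does not describe. All these sizes rest on normality, complete data and the assumed effects; missing marker samples would reduce power for every method.

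**What to change.** In 10.5.2, replace the chi-squared wording with:

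- (a) Marker level or change against CR/CRh: exact Wilcoxon rank-sum test.
- (b) Marker change against cytokine change, both as levels: Spearman correlation with 95% confidence interval.
- (c) A marker that is genuinely binary, for example detected or not on blot: Fisher's exact test against response, and Wilcoxon rank-sum against cytokine level, so that the cytokine is never cut.

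Apply this to PD-1, PD-L1 and PD-L2, and reconcile the PD-L2 assay between Sections 3.3 and 6.5. Before the data are seen, fix one cytokine summary for each phase (blinatumomab alone, Days 1 to 10; combination, Days 15 to 21) and the marker time points. Include the scheduled Cycle 2 Day 29 (+8) sample or give a reason for leaving it out. Section 6.2 also asks for a blot aspirate at that visit, which 6.5.1.2 does not list. If categories are kept, fix the cut-points in advance and use an exact test. Label the results exploratory and unadjusted for multiplicity.

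The cost is one paragraph and no new samples, with these limits:
- The cytokine summary must be chosen in advance.
- Multiplicity is large: 3 markers × 10 cytokines × 2 phases = 60 correlations, so 60 × 0.05 = 3 false positives expected if nothing is associated.
- Estimates stay imprecise. Using tanh(atanh(0.5) ± 1.96 × √((1 + 0.5²/2)/(n − 3))), a Spearman estimate of 0.5 has a 95% interval of about 0.10 to 0.76 at n = 24 and 0.01 to 0.80 at n = 18.
- CR requires fewer than 5% marrow blasts (7.1.4.1), so post-treatment lymphoblast markers may be unmeasurable mainly in responders. That comparison with response should be descriptive, with the number of measurable patients shown at each time point.

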11. STUDY MANAGEMENT

11.1 Conflict of Interest

Any investigator who has a conflict of interest with this study (patent ownership, royalties, or financial gain greater than the minimum allowable by their institution, etc.) must have the conflict reviewed according to UCSD conflict of interest policy.

11.2 Institutional Review Board (IRB) Approval and Consent

The IRB should approve the consent form and protocol prior to any study-related activities. It is expected that the IRB will have the proper representation and function in accordance with federally mandated regulations.

In obtaining and documenting informed consent, the investigator should comply with the applicable regulatory requirement(s), and should adhere to Good Clinical Practice (GCP) and to ethical principles that have their origin in the Declaration of Helsinki.

Before recruitment and enrollment onto this study, the patient will be given a full explanation of the study and will be given the opportunity to review the consent form. Each consent form must include all the relevant elements currently required by the FDA Regulations and local or state regulations. Once this essential information has been provided to the patient and the investigator is assured that the patient understands the implications of participating in the study, the patient will be asked to give consent to participate in the study by signing an IRB-approved consent form.

Prior to a patient's participation in the trial, the written informed consent form should be signed and personally dated by the patient and by the person who conducted the informed consent discussion.

11.3 Required Documentation

Before the study can be initiated at any site, the following documentation must be provided to the UC San Diego Clinical Trials Office.

- A copy of the official IRB approval letter for the protocol and informed consent
- IRB membership list
- CVs and medical licensure for the principal investigator and any associate investigators who will be involved in the study
- Form FDA 1572 appropriately filled out and signed with appropriate documentation (NOTE: this is required if {institution} holds the IND. Otherwise, the affiliate Investigator's signature on the protocol is sufficient to ensure compliance)
- A copy of the IRB-approved consent form
- CAP and CLIA Laboratory certification numbers and institution lab normal values
- Executed clinical research contract

11.4 Required Documentation (For multi-site studies)

Before the study can be initiated at any site, the following documentation must be provided to the UCSD Research Office.

- A copy of the official IRB approval letter for the protocol and informed consent document OR documentation of agreement to accept UCSD IRB approval of the protocol and consent through the UC IRB Reliance Registry by means of the UC Memorandum of Understanding
- IRB membership list or FWA letter
- CVs and medical licensure for the principal investigator and any associate investigators who will be involved in the study
- A copy of the IRB approved consent form
- CAP and CLIA Laboratory certification numbers and institution lab normal values
- Executed clinical research contract

11.5 Registration Procedures

All patients must obtain a study ID number from the UCSD BMT Clinical Trials Office before enrollment to study in the Velos EDC system. An eligibility check list signed by the PI or Sub-I must be faxed or emailed via secure email to the BMT Clinical Trials Office at [contact] or [contact]. Confirmation of eligibility is required prior to starting treatment.

Patients will be given a unique sequential patient ID number based on the study number, site number and patient enrollment number (1504-XX-XX).

UCSD BMT Clinical Trials Office staff will notify the outside site by fax or email via secure email of the patient's study number, and the randomization group of the patient.

Patient Eligibility Check list is located in **Appendix D**.

11.6 Data Forms and Submission Schedule

Data Forms Completion

- Data forms are to be completed following Screening, and then after each study visit.

Data Forms Submission

Data forms are to be completed in the Velos EDC system and corresponding source documentation uploaded within 2 weeks after each study visit. Timeline for Data Form submission is as follows:

- Screening Forms: to be completed within 24 hours following confirmation of eligibility and enrollment on the study.
- Treatment Visit Forms: within 2 weeks of the end of each visit, to include Con Med forms.
- Off-Study Form/Death Form: within 1 week of knowledge of off-study status or death of patient.
- AE Forms: to be updated at least every 2 weeks, but always prior to scheduled Study Conference Calls (scheduled monthly)
- SAE Forms: to be sent within 24 hours of knowledge of the event, and then as soon as a final report can be done.

11.7 Subject Data Protection

In accordance with the Health Information Portability and Accountability Act (HIPAA), subjects who have provided written informed consent must also sign a subject authorization to release medical information to the study Sponsor and allow a regulatory authority, or Institutional Review Board access to subject's medical information relevant to the study.

